8.2.2.3. Systemic Events

Prior to vaccination on Day 1, a baseline assessment of fatigue, headache, vomiting, nausea, diarrhea, muscle pain, and joint pain will be recorded in the e-diary.

During the reactogenicity e-diary reporting period, maternal participants will be asked to assess vomiting, diarrhea, headache, fatigue, chills, new or worsened muscle pain, and new or worsened joint pain and to record the symptoms in the reactogenicity e-diary. Based on local practice in certain countries/locales, a study staff member/field worker will call or visit maternal participants daily after vaccination to assess the presence of systemic events during the reactogenicity reporting period. The symptoms will be assessed by the maternal participant as absent, mild, moderate, or severe according to the grading scale in [Table 3](#).

Maternal participants will also be instructed to contact site staff if they visit the emergency room or are hospitalized for severe fatigue, headache, vomiting, nausea, diarrhea, muscle pain, or joint pain within 7 days after vaccination. Based on local practice in certain countries/locales, maternal participants will be referred to the appropriate healthcare facility at the discretion of the study staff/field worker if there are any concerns, as appropriate. In the event that the maternal participant does not call, the investigator or qualified designee will contact the maternal participant. The study staff/field worker may also contact the maternal participant to obtain additional information on events entered into the e-diary.

If a Grade 3 systemic event is reported in the reactogenicity e-diary, a telephone contact should occur to ascertain further details and determine whether a site visit is clinically indicated. Only an investigator or medically qualified person is able to classify a maternal participant's systemic event as Grade 4. If a maternal participant experiences a confirmed Grade 4 systemic event, the investigator must immediately notify the sponsor and, if it is determined to be related to the administration of the study intervention, further vaccinations will be discontinued in that maternal participant.

Table 3. Systemic Event Grading Scale

	Mild (Grade 1)	Moderate (Grade 2)	Severe (Grade 3)	Potentially Life Threatening (Grade 4)
Vomiting	1-2 times in 24 hours	>2 times in 24 hours	Requires IV hydration	Emergency room visit or hospitalization for hypotensive shock

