- Perform an obstetric ultrasound scan and/or record findings to confirm singleton pregnancy and rule out fetal abnormalities.
- Record nonstudy vaccinations as described in [Section 6.5](#).
- Collect and record concomitant medication associated with AE/SAEs.
- Ensure and document that all of the inclusion criteria and none of the exclusion criteria are met.
- Ensure that the participant meets none of the temporary delay criteria as described in [Section 5.5](#).
- Explain the e-diary technologies available for this study (see [Section 8.15](#)) and assist the participant in downloading the study application onto her own device or issue a provisioned device if required.
- Record systemic events at baseline in the e-diary.
- Assign a single participant identifier using the IRT system.
- Collect a blood sample (approximately 20 mL) for immunogenicity testing.
- Obtain a nasal (midturbinate) swab (collected by site staff).
- Obtain the participant's randomization number and study intervention allocation using the IRT system.
- Unblinded site staff member(s) will dispense/administer 1 dose of study intervention into the deltoid muscle of the (preferably) nondominant arm. Please refer to the IP manual for further instruction on this process.
- Blinded site staff must observe the participant for at least 30 minutes after study intervention administration for any acute reactions. Record any acute reactions (including time of onset) in the participant's source documents and on the AE page of the CRF, and on an SAE form as applicable.
- Ask the participant to contact the site staff or investigator if the participant experiences acute chest pain, shortness of breath, or palpitations (see [Section 8.14](#)).

- Issue a measuring device to measure local reactions at the injection site and a thermometer for recording daily temperatures and provide instructions on their use. Provide instructions on e-diary completion and ask the participant to complete the reactogenicity e-diary from Day 1 through Day 7, with Day 1 being the day of vaccination, OR explain to the maternal participant that a study staff member/field worker will call or visit her every day from Day 2 through Day 7 after vaccination (where Day 1 is the day of vaccination) to collect or take her temperature and record systemic events, acute local reactions, and use of antipyretic medication in a diary (if applicable).

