3.1.1.1. Local Reactions

The local reactions assessed and reported in the e-diary are redness, swelling, and pain at the injection site, from Day 1 through Day 7 after each dose, where Day 1 is the day of each dose. Maternal participants originally randomized to placebo who subsequently receive BNT162b2 1 month following delivery will not complete a reactogenicity e-diary after receiving BNT162b2.

This section describes derivations with details for the assessment of local reactions: presence, severity level, duration, and onset day.

Presence or Absence

For each local reaction and any local reaction on any day, Table 3 explains the algorithm to derive the presence of a reaction (yes or no) during the interval from Day 1 through Day 7, where Day 1 is the day of each dose.

Table 3. Derived Variables for Presence of Each and Any Local Reaction Within 7 Days for Each Dose

Variable	Yes (1)	No (0)
Presence of each local reaction.	Participant reports the reaction as “yes” on any day (Day 1 through Day 7).	For each local reaction, participant reports the reaction as “no” on all 7 days (Day 1 through Day 7) or as a combination of “no” and missing on all 7 days (Day 1 through Day 7).
Presence of any local reaction.	Participant reports any local reaction as “yes” on any day (Day 1 through Day 7).	For all 3 local reactions, participant reports “no” on all 7 days (Day 1 through Day 7) or as a combination of “no” and missing on all 7 days (Day 1 through Day 7).

Note: Missing e-diary data will not be imputed. Participants with no e-diary data reported will not be included in the e-diary summaries.

Severity and Maximum Severity

Redness and swelling will be measured and recorded in measuring device units (range: 1 to 21) and then categorized during analysis as absent, mild, moderate, or severe based on the grading scale in Table 4. Measuring device units can be converted to centimeters according to the following formula: 1 measuring device unit = 0.5 cm. Pain at the injection site will be assessed by the participant as absent, mild, moderate, or severe according to the grading scale in Table 4.

Table 4. Local Reaction Grading Scale

	Mild (Grade 1)	Moderate (Grade 2)	Severe (Grade 3)	Potentially Life Threatening (Grade 4)
Pain at the injection site	Does not interfere with activity.	Interferes with activity.	Prevents daily activity.	Emergency room visit or hospitalization for severe pain.

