Redness	>2.0 cm to 5.0 cm (5 to 10 measuring device units).	>5.0 cm to 10.0 cm (11 to 20 measuring device units).	>10 cm (≥21 measuring device units).	Necrosis or exfoliative dermatitis.
Swelling	>2.0 cm to 5.0 cm (5 to 10 measuring device units).	>5.0 cm to 10.0 cm (11 to 20 measuring device units).	>10 cm (≥21 measuring device units).	Necrosis.

For each local reaction reported for each dose, the maximum severity grade will be derived for the e-diary collection period (Day 1 through Day 7, where Day 1 is the day of each dose) as follows:

maximum severity grade = highest grade (maximum severity) within 7 days after vaccination (Day 1 through Day 7) among severity grades where the answers are neither “no” nor missing for at least 1 day during the interval from Day 1 through Day 7.

Duration (First to Last Day Reported)

For participants experiencing any local reactions (or those with a derived reaction as described in [Table 4](#)), the maximum duration (last day of reaction – first day of reaction + 1) will be derived for each study vaccination. Resolution of the reaction is the last day on which the reaction is recorded in the e-diary or the date the reaction ends if it is unresolved during the participant e-diary recording period (end date collected on the CRF), unless chronicity is established. If there is no known end date, the duration will be considered unknown and set to missing. However, if a reaction is ongoing at the time of a subsequent vaccination, the end date/day for the ongoing reaction would be the date/day that the next vaccine is administered, which will be used for the duration computation. Participants with no reported reaction have no duration.

Onset Day

The onset day of each local reaction will be derived. Onset day is defined as the first day after vaccination that a reaction is reported of any severity.

For the onset day of each local reaction, if participants report a change in severity of the local reaction, only the first day of reporting that specific local reaction will be counted.

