3.1.1.2. Systemic Events (Systemic Event Symptoms and Fever)

The systemic events assessed and recorded in the e-diary are fever, vomiting, diarrhea, headache, fatigue/tiredness, chills, new or worsened muscle pain, and new or worsened joint pain from Day 1 through Day 7, where Day 1 is the day of each dose. The derivations for systemic events will be handled in a way similar to the handling of local reactions with respect to presence of event, severity level, duration, and onset day (see [Section 3.1.1.1](#)).

The symptoms will be assessed by the participant as absent, mild, moderate, or severe according to the grading scale in [Table 5](#).

Table 5. Systemic Event Grading Scale

	Mild (Grade 1)	Moderate (Grade 2)	Severe (Grade 3)	Potentially Life Threatening (Grade 4)
Vomiting	1-2 times in 24 hours.	>2 times in 24 hours.	Requires IV hydration.	Emergency room visit or hospitalization for hypotensive shock.
Diarrhea	2 to 3 loose stools in 24 hours.	4 to 5 loose stools in 24 hours.	6 or more loose stools in 24 hours.	Emergency room visit or hospitalization for severe diarrhea.
Headache	Does not interfere with activity.	Some interference with activity.	Prevents daily routine activity.	Emergency room visit or hospitalization for severe headache.
Fatigue/tiredness	Does not interfere with activity.	Some interference with activity.	Prevents daily routine activity.	Emergency room visit or hospitalization for severe fatigue.
Chills	Does not interfere with activity.	Some interference with activity.	Prevents daily routine activity.	Emergency room visit or hospitalization for severe chills.
New or worsened muscle pain	Does not interfere with activity.	Some interference with activity.	Prevents daily routine activity.	Emergency room visit or hospitalization for severe new or worsened muscle pain.
New or worsened joint pain	Does not interfere with activity.	Some interference with activity.	Prevents daily routine activity.	Emergency room visit or hospitalization for severe new or worsened joint pain.

Abbreviation: IV = intravenous.

Oral temperature will be collected in the evening, daily, for 7 days following each dose (Days 1 through 7, where Day 1 is the day of each dose) and at any time during the 7 days that fever is suspected. Fever is defined as an oral temperature of $\geq 38.0^{\circ}\text{C}$ (100.4°F). The highest temperature for each day will be recorded in the e-diary.

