6.1.1.2. Systemic Events

6.1.1.2.1. Main Analysis

- Estimand: The percentage of maternal participants reporting systemic events (fever, fatigue, headache, chills, vomiting, diarrhea, new or worsened muscle pain, and new or worsened joint pain) within 7 days after each dose ([Section 2.1](#)).
- Analysis set: Safety population (maternal) ([Section 4](#)).
- Analysis time point: Within 7 days after each dose.
- Analysis methodology: Descriptive statistics ([Section 5.2.1](#)).
- Intercurrent events and missing data: The participants without any e-diary data throughout the 7 days after vaccination will be excluded from the analysis at that particular vaccination; missing values will not be imputed.
- Reporting results: Descriptive statistics for each systemic event after each dose in each vaccine group will be presented by maximum severity and cumulatively across severity levels. Descriptive summary statistics will include counts and percentages of participants with the indicated endpoint and the associated 2-sided Clopper-Pearson 95% CIs.

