6.1.1.2.2. Supplementary Analyses

The following endpoints for assessment of systemic events will be summarized similarly to the assessment of local reactions:

- Duration of each systemic event after each dose.
- Onset day of each systemic event after each dose.

These continuous endpoints will be summarized by displaying n, mean, median, standard deviation, minimum, and maximum for each vaccine group.

The use of antipyretic medication (see [Section 3.1.1.3](#)) will be summarized similarly to systemic events, except that there is no severity level associated with the use of antipyretic medication.

In addition, the proportions of participants reporting each prompted systemic event after any dose will be summarized by maximum severity level.

Figures:

Bar charts with the proportions of participants for each systemic event throughout 7 days after each dose will be plotted for each vaccine group. The bars will be divided into severity categories to highlight the proportions of participants by severity.

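### The SAP does not use the systemic symptoms recorded before Dose 1, so symptoms already present at injection (mainly fatigue and headache) enter the per-arm reactogenicity rates, onset days and durations

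*SAP*

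**What the plan says.** **Collection.** Protocol 8.2.2.3 requires that, before vaccination on Day 1, "a baseline assessment of fatigue, headache, vomiting, nausea, diarrhea, muscle pain, and joint pain will be recorded in the e-diary". The Visit 1 procedures in Protocol 8.11.1 include the step "Record systemic events at baseline in the e-diary", and the schedule in 1.3.1 marks it at Visit 1 only. The Visit 2 procedures have no such step.

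**Definition.** SAP 3.1.1.2 lists the systemic events as "fever, vomiting, diarrhea, headache, fatigue/tiredness, chills, new or worsened muscle pain, and new or worsened joint pain from Day 1 through Day 7". The new-or-worsened condition is attached to muscle and joint pain and to nothing else. The section then says: "The derivations for systemic events will be handled in a way similar to the handling of local reactions".

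**Derivation.** The borrowed rules are in SAP 3.1.1.1. Table 3 makes a reaction present if it is reported on any day of the 7-day window. For onset, "Onset day is defined as the first day after vaccination that a reaction is reported of any severity". Duration is last day minus first day plus 1. None of these rules refers to the pre-dose record.

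**Reporting.** In SAP 6.1.1.2.1, "Descriptive statistics for each systemic event after each dose in each vaccine group will be presented by maximum severity", with per-group Clopper-Pearson intervals. SAP 6.1.1.2.2 adds duration and "Onset day of each systemic event after each dose". The baseline summaries in SAP 6.6.1 cover demographics and medical history. SAP 3.5 defines baseline in general terms but assigns the symptom record no role.

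**The concern.** The derivation was built for injection-site signs, which have no state before the injection. Fatigue, headache, vomiting and diarrhea do have one, and the women enrolled are 24 to 34 weeks pregnant. Symptoms that a woman already had can therefore be tabulated as events after vaccination.

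The plan is also uneven. The baseline question covers fatigue and headache as well as muscle and joint pain, but only the last two must be new or worsened to count.

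Describing tolerability in pregnancy is a primary objective. Protocol 2.2.1 quotes single-arm reactogenicity rates from the nonpregnant study (fatigue 62.9%, headache 55.1%), and readers are likely to set the pregnant vaccine-arm percentages beside them. Without a baseline table they cannot see how much was there before the injection.

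**Working it through.** The documents state no figure to reproduce. The check traces the rules and then sizes the effect under stated assumptions.

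**Step 1: trace the rules.** Take a woman who records a headache before Dose 1 and reports it unchanged on Days 1 to 7, when it ends. Presence is yes, maximum severity is her usual grade, onset is Day 1 and duration is 7 − 1 + 1 = 7 days. If her pre-dose headache is absent on Day 1 and returns later, it still counts, with the later day as onset. A woman with unchanged muscle pain is not counted.

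**Step 2: size in the per-arm rates.** Let b be the share of women who would report the symptom on Days 1 to 7 without vaccine, and v the vaccine-caused rate, independent of b. Both are assumed.

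- Placebo arm: b
- Vaccine arm: b + (1 − b)v
- Difference: (1 − b)v

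| v | b (placebo) | Vaccine arm | Difference |
|---|---|---|---|
| 40% | 10% | 46% | 36 points |
| 40% | 30% | 58% | 28 points |
| 40% | 50% | 70% | 20 points |
| 62.9% | 10% | 66.6% | 56.6 points |
| 62.9% | 30% | 74.0% | 44.0 points |
| 62.9% | 50% | 81.5% | 31.5 points |

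The value 62.9% is the fatigue rate from the nonpregnant study, used only as an example. With it, the vaccine-arm rate exceeds v by 3.7, 11.1 and 18.6 points. For scale, with 175 women per group (Protocol 9.2), a placebo rate of 30% has a Clopper-Pearson interval of about 23% to 37%.

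**Step 3: what the planned output already allows.** Under this model v = (vaccine rate − b)/(1 − b). For v = 40%: (0.46 − 0.10)/0.90 = (0.58 − 0.30)/0.70 = (0.70 − 0.50)/0.50 = 0.40. The two planned percentages therefore recover v, provided independence holds. No such step exists for onset day or duration, which are summarized within each arm.

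**Step 4: what the baseline record can remove.** It identifies only the part of b present at the pre-dose record; call it c, with c ≤ b. Among women free of the symptom at baseline, placebo would report (b − c)/(1 − c). Assume b = 30%, half of it present at baseline (c = 15%), and v = 40%. Placebo is 0.15/0.85 = 17.6%, and vaccine is 0.176 + 0.824 × 0.40 = 50.6%, against 30% and 58% in the planned tables. Background is reduced, not removed.

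**The case against.** The strongest reply is that the design already handles background symptoms. The trial is randomized 1:1, observer-blind and saline-controlled, and the estimand is the percentage of women reporting an event, not the percentage caused by vaccine. The planned derivation matches that estimand, and (1 − b)v is the correct risk difference for it. This stands. A reader might infer that carried-over symptoms bias the vaccine-placebo comparison. The documents do not support that, because both arms have the same expected background.

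Four further points limit the concern, and all stand:

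- **Vomiting and diarrhea.** Temporary delay criterion 1 (Protocol 5.5) lists both among current symptoms that could represent COVID-19, and it is checked before each dose. Few women should have them at injection. Fatigue and headache are not listed.
- **Between-group difference.** A reader of 6.1.1.2.1 alone might conclude that none is planned. SAP 5.2.1 gives a Miettinen-Nurminen interval for binary endpoints generally, and 6.1.1.2.1 cites 5.2.1. Only the reporting line is silent, whereas the AE section (6.1.1.3.1) asks for the difference expressly.
- **Onset and duration.** It is tempting to say that every carried-over symptom gets Day 1 onset and full duration. The rule uses the first day reported, so an intermittent symptom can start later, and the duration rule makes an exception for established chronicity.
- **Reach of the baseline data.** It is one assessment before one dose. It cannot fully separate background from vaccine effect, and the documents show neither the e-diary wording nor whether baseline grade was recorded.

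The placebo argument does not cover the within-arm onset and duration summaries, or the vaccine-arm percentage read alone.

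**Conclusion.** The omission is real and limited. The SAP leaves unused a pre-dose record that the protocol collects, so symptoms present before injection, chiefly fatigue and headache, are mixed into the per-arm percentages, onset days and durations. This affects how those figures are interpreted, not the validity of the randomized comparison or of the primary estimand.

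The size cannot be stated from the documents. The figures above rest on assumed background rates of 10% to 50%, assumed vaccine-caused rates and independence between the two. The direction is more certain than the size: background raises each arm's percentage and shrinks the absolute difference.

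The change is worth making because it is cheap and uses data already collected.

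**What to change.** Make two supplementary additions to SAP 6.1.1.2.2 and one clarification to 6.1.1.2.1. The primary estimand stays as it is.

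1. Tabulate baseline systemic events by vaccine group.
2. For Dose 1, summarize fatigue, headache, vomiting and diarrhea that were absent at baseline, or of higher grade than at baseline if grade was recorded. Report onset day and duration on the same basis. State whether the denominator is all women or those free of the symptom at baseline, because the two give different percentages.
3. State in the reporting line of 6.1.1.2.1 that the between-group difference will be shown with the Miettinen-Nurminen interval already described in SAP 5.2.1.

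**Cost.** A few extra outputs from existing e-diary data and one sentence, with no new collection. No primary endpoint definition changes.

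**Downsides.** The summary covers Dose 1 only, and chills have no baseline record. Background symptoms that begin after the pre-dose record remain. If no baseline grade exists, true worsening of a pre-existing symptom is left out. For these reasons it must stay supplementary.

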3.1.1.3. Use of Antipyretic Medication

The use of antipyretic medication is also recorded in the e-diary from Day 1 through Day 7, where Day 1 is the day of each dose. For the use of antipyretic medication from Day 1 through Day 7 after each dose, the following endpoints and variables will be derived for analysis following the same rules as for local reactions (see [Section 3.1.1.1](#)), where applicable.

- Presence (yes or no) of use of antipyretic medication on each day (Day 1 through Day 7)
- Presence (yes or no) of use of antipyretic medication on any day (Day 1 through Day 7)
- Duration (first to last day reported) of use of antipyretic medication
- Onset day of use of antipyretic medication

The use of antipyretic medication will be summarized and included in the systemic event summary tables but will not be considered a systemic event.

3.1.1.4. Adverse Events

For maternal participants, AEs will be assessed from the time of informed consent through 1 month after Dose 2. Additionally, for those maternal participants who originally received placebo and subsequently receive BNT162b2, AEs will be collected from the first dose through 1 month after the second dose of BNT162b2. AEs will be categorized according to MedDRA terms.

The primary safety endpoint “AEs from Dose 1 through 1 month after Dose 2” and other AE endpoints will be summarized by SOC and PT at the participant level.

This primary safety endpoint will be supported by summaries and listings of related AEs, severe AEs, and immediate AEs (within the first 30 minutes after each dose). AE reporting will be based on the specific reporting period. Missing AE start dates will be imputed following the Pfizer data standard rules as described in [Section 5.3](#).

